9.2.5 Day of Discharge

- Physical examination
- Vital signs
- Performance Status
- Blood sample for panitumumab-IRDye800 antibody pharmacokinetics
- Assessment for adverse events
- Assessment for concomitant medications

9.2.6 Day 15 (\pm 4 days)

- Physical examination
- Vital signs (blood pressure, heart rate, respiratory rate, temperature)
- Performance Status
- Serum magnesium and phosphorus; any other blood tests as needed to assess for any ongoing abnormalities, per PIs discretion
- CBC and platelets
- Blood sample for future assessment of immunogenicity
- Blood sample for panitumumab-IRDye800 antibody pharmacokinetics
- Assessment for adverse events
- Assessment for concomitant medications

9.2.7 Day 30 (\pm 4 days)

- Investigator or study staff will contact the subject by telephone or review of electronic medical record data to collect any additional adverse events that are attributable to the study and/or concomitant medications.

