7.3 Assessment of Causality

For any AE that occurs during this study, it will be the responsibility of the Investigator to assess the relationship of the event to study treatment.

For this clinical trial, the following criteria will be used:

- **Unrelated:** There is no temporal relationship between the event and the administration of the study drug, and/or the event is clearly due to the subject's medical condition, other therapies, or accident.
- **Possibly Related:** There is some temporal relationship between the event and the administration of the study drug and the event is unlikely to be explained by the participant's medical condition or other therapies.
- **Probably Related:** The temporal relationship between the event and the administration of the study drug is compelling, and the participant's medical condition or other therapies cannot explain the event.
- **Definitely Related:** The temporal relationship between the event and the administration of the study drug is compelling, the participant's medical condition or other therapies cannot explain the event and the event follows a known or suspected response pattern to the medication.

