7.5 Safety Monitoring and Reporting

7.5.1. Monitoring and Recording of Adverse Events

Both serious and non-serious AEs will be clearly noted in source documentation and listed on study-specific Case Report Forms (CRFs). The PD or designee will assess each AE to determine whether it is unexpected according to the Informed Consent, Protocol Document, or Investigator's Brochure, and related to the investigation.

All adverse events (AEs), regardless of seriousness or relationship to study drug, are to be collected only on designated study dates from signing of informed consent through 30 days after administration of study drug, and recorded in the study-specific worksheets, with the following exceptions:

- AEs that are solely laboratory values; are not related to the study drug; AND are clinically non-significant may not be collected.

- Non-serious AEs that occur within 30 (+/-7) days after surgical resection of the tumor; are not related to the study drug; are not clinically significant; AND are expected in the post-surgery clinical setting may not be collected.
- SAEs that occur from signing of informed consent to prior to Day 1 may not be collected unless assessed as possibly, probably or definitely related to a study procedure.

All patients enrolled in this study receive surgical intervention in the course of their standard of care. As a consequence of this surgery, patients may experience certain expected and normal adverse events. The following post-operative adverse events will be captured only in the patient's Electronic Health Record (EHR) source documentation and not in the adverse event log. If the adverse event exceeds the grading listed below or occurs outside the post-operative time window, the adverse event will be recorded in the Adverse Event Logs.

- Surgical wound site and associated, expected secondary signs and symptoms, including:
 - CTCAE v5.0 Grade 1 erythema, edema, and pruritis.
 - CTCAE v5.0 Grade 1 pain associated with surgical wound, including headaches – mild pain, little to no limit on adult daily life.
 - CTCAE v5.0 Grade 1 nausea, vomiting, and dysphagia.
 - CTCAE v5.0 Grade 1 weight loss, anemia, and electrolyte abnormalities.
 - CTCAE v.5.0 Grade 2 trismus.

Whenever possible, symptoms should be grouped as single syndrome or diagnosis. The Investigator should specify the date of onset, maximal intensity, corrective therapy given, outcome, and his/her assessment of causality.

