7.5.2. Reporting Adverse Events and Serious Adverse Events

Non-serious adverse events will be reported annually to FDA via an Annual Report (IND 119474) and to IRB via Continuing Review.

The PD (aka Principle Investigator) must immediately report within 24 hours of knowledge of event to the Sponsor (ie, IND Holder, [name]), any serious adverse event, whether or not considered related to study drug. SAEs of all grades will be reported to the Sponsor using the Stanford Cancer Institute SAE CRF. The investigator must provide a detailed description of the event, the treatment regimen, relevant laboratory and evaluations and assessment of the relationship of the AE to the study drug. All relevant information should be reported as it becomes available.

SAEs CTCAE Grade 3 and above, and all subsequent follow-up reports will be reported to the Stanford Cancer Institute Data and Safety Monitoring Committee (DSMC) using the study specific CRF regardless of the event's relatedness to the investigation. Following review by the DSMC, events meeting the IRB definition of an "Unanticipated Problem" (UP) will be reported

to the IRB using eProtocol within 10 working days of DSMC review, or within 5 working days for deaths or life-threatening experiences.

Adverse events deemed serious, unexpected (ie, not described in the protocol, Investigator's Brochure or informed consent documents) and related to study drug must be reported to Sponsor using the FDA MedWatch form 3500a within 24 hours of knowledge of event. The Sponsor is responsible for deciding whether the event meets IND Safety Reporting criteria.

Events will be submitted to Sponsor [name], at:

[name]
Professor of Otolaryngology-Head and Neck Surgery & Radiology		
[name]
[name]
[name]
[contact]		94305

It will be the responsibility of the Sponsor to provide to the FDA all information concerning significant hazards, contraindications, side effects or precautions felt significant to the safety of the drug being studied. The PD is responsible for accurate and timely communication to the Sponsor of any events reportable to FDA. Subjects will be instructed prior to participation on the importance of reporting any symptoms (new or worsening), and/or any physical changes throughout their participation in the study. These events will be recorded accordingly in the CRF. Abnormal laboratory and/or clinical assessments will also be captured in the appropriate CRF.

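### Section 9.2.7 limits the Day 30 contact to study-attributable adverse events, which contradicts the collect-all rule in Section 7.5.1 and calendar footnote 15

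*Combined protocol and SAP*

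**What the plan says.** The general rule is in Section 7.5.1: "All adverse events (AEs), regardless of seriousness or relationship to study drug, are to be collected only on designated study dates", from consent "through 30 days after administration of study drug". The exceptions that matter late in follow-up are narrow:

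- Laboratory findings: "AEs that are solely laboratory values; are not related to the study drug; AND are clinically non-significant may not be collected".
- Post-operative events: "Non-serious AEs that occur within 30 (+/-7) days after surgical resection of the tumor; are not related to the study drug", provided that they are also not clinically significant and are expected after surgery.
- A short list of low-grade surgical effects (Grade 1 items and Grade 2 trismus), which stay in the health record and out of the AE log.

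Section 7.5.2 requires the Sponsor to be told, within 24 hours of knowledge, of "any serious adverse event, whether or not considered related to study drug". Section 7.3 says of causality that "it will be the responsibility of the Investigator to assess the relationship of the event to study treatment".

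The calendar in Section 9.1 marks AEs at Day 30, and its footnote 15 points that row to Section 7.5.1 without any limit by attribution.

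Section 9.2.7 then describes the Day 30 contact: "Investigator or study staff will contact the subject by telephone or review of electronic medical record data", the purpose being "to collect any additional adverse events that are attributable to the study and/or concomitant medications". The lists for Day 0, the day before surgery, the day of surgery, discharge and Day 15 (Sections 9.2.2 to 9.2.6) each call for an AE assessment with no such limit.

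**The concern.** Whether an event is attributable should be decided after it is recorded. Section 9.2.7 makes attribution a condition of collection, so an event judged unrelated at that point leaves no entry to grade, review or reclassify.

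This matters more here than in many trials. Every subject has surgery 1 to 5 days after infusion, so a surgical explanation for a late event will often be available. The word used in 9.2.7 is not one of the four causality categories in Section 7.3 and has no stated threshold. Even the lowest related category in 7.3 requires that other explanations be unlikely. A filter of this kind tends to remove late events from the safety record, and the direction of that error favours the agent. Because Section 7.5.1 confines collection to designated dates, there is no later scheduled date on which a missed event would be picked up.

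**Working it through.** The plan gives no figure on this point, so there is none to reproduce. The check sets the texts side by side and does date arithmetic on the visit windows.

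**1. Do the texts conflict?**
- Section 7.5.1: relationship does not matter, except within the listed exceptions.
- Calendar, Day 30 column with footnote 15: the rule is Section 7.5.1.
- Section 9.2.7: relationship decides what is collected.

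The closing words of 9.2.7 on concomitant medications can mean AEs attributable to those medications, or collection of the medications themselves. AEs remain limited by attribution on either reading, so the conflict stands.

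**2. Which days depend on the Day 30 contact alone?**
- Day 15 visit, ±4 days: 15 − 4 = Day 11 to 15 + 4 = Day 19.
- Days left to Day 30: 30 − 19 = 11 to 30 − 11 = 19 (nominally 30 − 15 = 15).
- As calendar time: 11/30 = 37% to 19/30 = 63% of the 30 days.
- Using the contact's own ±4 days (Day 26 to 34), the gap from visit to contact is 26 − 19 = 7 to 34 − 11 = 23 days.

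Section 9.2.5 also lists an AE assessment at discharge. A subject discharged after the Day 15 visit has a shorter interval, so 11 to 19 days is the range when discharge comes first.

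**3. Which events are lost?** Take a late event judged unrelated.
- Non-serious, not clinically significant and expected after surgery: already exempt under 7.5.1. With surgery on Day 1 to 5, that exemption nominally ends on Day 31 to 35 (1 + 30 to 5 + 30), so it spans the interval. At its shortest it ends on Day 24 (1 + 23).
- Laboratory value only and clinically non-significant: already exempt.
- Non-serious but clinically significant or unexpected: kept by 7.5.1, dropped by 9.2.7.
- Serious and known to the team: still reportable under 7.5.2.
- Serious and not otherwise known: kept by 7.5.1, but not asked for under 9.2.7.

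The loss is the third and fifth groups.

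**4. Do the follow-up windows agree?**
- Section 7.5.1: through 30 days.
- Sections 9.1 and 9.2.7: Day 30 ±4, so the earliest contact is Day 26, which leaves 30 − 26 = 4 days uncovered.
- Section 4.8: 30 ±7 days, so the earliest end is Day 23.
- Section 4.7: off study after a 30-day observation period.

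These do not agree.

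**The case against.** The best reply is that other text limits the damage. The calendar footnote sends a site to the full rule. Section 7.5.2 has subjects told to report any new or worsening symptom throughout participation, with those events entered in the CRF, and Section 4.8 provides a 24-hour number. Minor surgical events are exempt by design. The agent is a single dose with an expected half-life of about 2.3 days or less, and safety is neither the primary nor the secondary endpoint. All of this stands, and it makes the point a modest one. It does not settle which text governs the Day 30 contact, and unsolicited reports do not replace asking.

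Four stronger readings are tempting, but the documents do not support them.

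- **A readmission in the filtered period would be hidden from the Sponsor and the safety committee.** Hospitalization makes an event serious. Section 7.5.2 sends any SAE the team learns of to the Sponsor, and SAEs of Grade 3 or above to the committee, whatever the relationship. Section 9.2.7 does not switch that off.
- **Study staff are given the causality assessment.** Section 9.2.7 says who makes the contact or reviews the record. It does not say who judges attribution, and Section 7.3 leaves that with the Investigator.
- **Detection of dose-limiting toxicity is materially affected.** Sections 2.4.2.2 and 4.4 require relatedness, so a filter that keeps attributable events keeps those judged to be dose-limiting. Only an earlier misattribution could lose one, and only where the Day 15 visit falls on Day 11 to 14 with no later discharge.
- **37% to 63% of events are lost.** That range is a share of calendar time. The documents give no rate for late events, so the number lost cannot be estimated.

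**Conclusion.** The contradiction is in the current text and should be corrected. As written, Section 9.2.7 puts an attribution filter on the last scheduled safety contact, against Section 7.5.1 and calendar footnote 15. The exposure is 11 to 19 days before Day 30 per subject, assuming that the Day 15 visit is held within its window and that discharge does not come after it. The events at risk are those judged unrelated that 7.5.1 keeps: clinically significant or unexpected non-serious AEs, and SAEs that the team does not learn of by another route. The primary and secondary endpoints are untouched. The mismatch in follow-up windows is a smaller, related inconsistency, worth up to 4 of the 30 days under the ±4-day window.

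**What to change.** Reword Section 9.2.7 so that the Day 30 contact collects all AEs and SAEs since the last visit, subject only to the exceptions in Section 7.5.1, with causality then assessed by the Investigator under Section 7.3. If concomitant medications are meant to be collected at the same contact, say so in a separate clause.

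State one follow-up window and use it in Sections 4.8, 7.5.1, 9.1 and 9.2.7. If AE collection is to run through 30 days as 7.5.1 says, the window must not let the final contact close the record before then. If an earlier contact is acceptable, 7.5.1 should say that collection ends at the contact.

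The cost is a few sentences of amendment and a few more unrelated events to log. The telephone call or record review is already planned, and no visit or procedure is added.

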9.3 Description of Evaluations / Procedures

- 9.3.1 Laboratory Evaluations:** Blood specimens will be collected for CBC; platelets; basic metabolic profile; magnesium and phosphorus; and serum pregnancy if necessary. Blood will be taken for fluorescent-labeled antibody pharmacokinetics and blood will be obtained and banked for future analysis of immunogenicity against the study drug as requested by the FDA in pre-IND conversations.
- 9.3.2 Physical Examinations:** A physical examination will be conducted to include review of all major systems prior to enrollment to study. Standard head and neck examination and system-oriented physical examination will be conducted on other visits.
- 9.3.3 Medical History:** A complete medical history including age; sex; race; current medications; any current or previous medical conditions; any previous surgeries; smoking history; alcohol use will be done at screening.
- 9.3.4 Vital Signs:** Vital signs including blood pressure; heart rate; respiratory rate; and temperature will be collected at each clinic visit. Height and weight will be collected at screening.
- 9.3.5 Cardiac Monitoring:** An ECG will be obtained during the screening period. A previous ECG that was obtained as part of standard of care may be used as the baseline ECG if obtained within 21 days prior to infusion. QT/QTc interval will be assessed at screening.

10. MEASUREMENTS

10.1 Primary Outcome Measure

The **primary objective** of the study is to determine if near-infrared fluorescence imaging of panitumumab-IRDye800 can identify metastatic disease in regional neck LNs of subjects with HNSCC.

The **primary endpoint** is: The number and location of panitumumab-IRDye800 positive LNs that are also tumor-positive at (histo-)pathology.

10.2 Secondary Outcome Measure

The **secondary objective** of the study is to determine if panitumumab-IRDye800 can identify LNs with the same accuracy as Lymphoseek.

The **secondary endpoint** is: The number and location of Lymphoseek positive LNs that are also tumor-positive at (histo-)pathology. Comparison of the number and location of Lymphoseek positive LNs that are also tumor-positive at (histo-)pathology vs the number and location of panitumumab-IRDye800 positive LNs that are also tumor-positive at (histo-)pathology.

11. REGULATORY CONSIDERATIONS

11.1 Institutional Review of Protocol

The protocol, the proposed informed consent and all forms of participant information related to the study (eg, advertisements used to recruit participants) will be reviewed and approved by the Stanford IRB and Stanford Cancer Institute Scientific Review Committee (SRC). Any changes

made to the protocol will be submitted as a modification and will be approved by the IRB prior to implementation. The PD will disseminate the protocol amendment information to all participating investigators.

The protocol and any significant amendments will be submitted to FDA. The PD is responsible for informing the Sponsor of protocol amendments.

11.2 Data and Safety Monitoring Plan

The Stanford Cancer Institute Data and Safety Monitoring Committee (DSMC) will be the monitoring entity for this study. The DSMC will audit study-related activities to determine whether the study has been conducted in accordance with the protocol, local standard operating procedures, FDA regulations, and Good Clinical Practice (GCP). This may include annual review of the following types of documents participating in the study: regulatory binders, case report forms, eligibility checklists, and source documents. In addition, the DSMC will regularly (monthly) review any DLTs, serious adverse events, and protocol deviations associated with the research to ensure the protection of human subjects. Results of the DSMC audit will be communicated to the IRB and the appropriate regulatory authorities at the time of continuing review, or in an expedited fashion, as needed.

11.3 Data Management Plan

The PD, or designees noted in the Delegation of Authority Log, will maintain adequate and accurate participant case histories with observations and other data pertinent to the study. Original source documents will be transcribed to Case Report Forms (CRFs). Source documents include hospital records, clinical charts, laboratory and pharmacy records, and recorded electronic data. Case report forms will be developed using the OnCore database system and maintained by the study team. CRFs will be kept in a locked office, only accessible to the research team.

12. STATISTICAL CONSIDERATIONS

12.1 Statistical Design

12.1.1. Primary Objective and Endpoint

The **primary objective** of the study is to determine if near-infrared fluorescence imaging of panitumumab-IRDye800 can identify metastatic disease in regional neck LNs of subjects with HNSCC.

The **primary endpoint** is: The number and location of panitumumab-IRDye800 positive LNs that are also tumor-positive at (histo-)pathology.

To **answer the primary objective**, we will calculate the sensitivity and specificity of the intraoperative findings on whether the LN is fluorescent (ie, presence of panitumumab-IRDye800) to the histopathological (gold standard) status of the LNs.

We will use the matched pair Durkalski's test (80), accounting for the cluster-correlation within subject, for all sensitivity and specificity comparisons (primary and secondary) using the clust.bin.pair package (81) in the R statistical software (84). Significance for both primary and secondary analyses will be assessed at the 0.05 level and to assess uncertainty, 95% confidence intervals will be provided for all estimates.

Descriptive statistics for continuous characteristics (eg, size of the tumor compartment) will include mean, standard deviation, median, interquartile range, minimum, and maximum values. Frequencies and percentages will be used to summarize categorical data. Graphical tools such as heat maps, histograms, and boxplots will be used to assess distributional properties of continuous variables.

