We propose to evaluate the fluorescently-labelled anti-EGFR antibody, panitumumab-IRDye800, for its ability to intraoperatively identify sentinel and LN (micro-)metastasis. We propose to directly compare fluorescence imaging of panitumumab-IRDye800 imaging findings to that of SNB and neck dissection whereby we will use (histo-)pathology as gold standard for determining the true tumor-positive LNs.

Potential benefits of panitumumab-IRDye800 for metastatic LN identification over SNB:

- 1) Panitumumab-IRDye800 is a tumor-targeted tracer that can allow intraoperative identification of metastatic lymph nodes (for the other techniques pathology is required to confirm).
- 2) Panitumumab-IRDye800 is systemically injected, and thus can allow metastatic LN identification also at sites that are not-accessible for a SN tracer (ie, tumor in the hypopharynx).
- 3) Panitumumab-IRDye800 provides a tumor-specific approach whereas the SN tracer is not tumor-specific.
- 4) Panitumumab-IRDye800 can be injected several days before the operation and thus scheduling logistics would be improved (SN tracer is preferable injected the day of surgery)
- 5) If successful with the optical dye, similar studies could be conducted with a radiolabeled dye.

Fluorescent, tumor-targeted antibodies for intraoperative cancer detection: Clinical data has provided evidence that novel tumor-targeted antibodies can improve detection, and survival in a variety of cancer types (48). By fluorescently labelling these antibodies (eg, using the near-infrared fluorescent dye IRDye800) it was shown that the sensitivity and specificity of (microscopic) tumor detection in the operative setting could be significantly improved (49–52). Improved visualization can thus significantly improve surgical techniques and outcome.

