2.4 Study Design

- The primary purpose for the protocol is **Image Guidance**. The primary objective of the study is to determine if near-infrared fluorescence imaging of panitumumab-IRDye800 can identify metastatic disease in regional neck LNs of subjects with HNSCC.
- There are **2 cohorts**.
- The study is **open-label**. No masking is used.
- The study is **non-randomized**.
- The primary outcome is **number and location of LNs that are near-infrared fluorescent and that contain tumor as defined by (histo-)pathology**.

The study is an open-label study to determine if near-infrared fluorescence imaging of panitumumab-IRDye800 can identify metastatic disease in regional neck LNs of subjects with HNSCC. Panitumumab-IRDye800-based findings will be compared to LN biopsy and neck dissection. A schematic overview of the clinical trial is given in Figure 1.

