3. Hereafter, as per standard of care, the surgeon will perform SNB using the gamma probe. For this, the surgeon will evaluate the neck with the gamma probe for the presence of radioactive nodes. Upon localizing of radioactive nodes, the count rate of the node will be determined. Then, just prior to the resection of the radioactive node, *in situ* fluorescence imaging will be performed to evaluate the fluorescence-based visibility of the node. For each radioactive node, the respective *in situ* location will be documented (level Ia, Ib, IIa, IIb, III, IV or V) as well as the radioactive status (count rate) and fluorescence status (yes/no). Hereafter the node will be harvested by the surgeon. This process will be repeated until no radioactive nodes are detected anymore *in situ*.

Step 2) Wound bed imaging:

As per standard of care SNB, upon completion of SNB, the neck will be screened once more with the gamma probe as such to determine the presence of any remaining radioactivity (ie, a radioactive signal detected > 10% of the background that correlates with any substrate (node). Areas in the wound bed determined radioactive-positive will be surgically re-evaluated, and, upon checking the fluorescence-status, removed, if deemed necessary by the surgeon. If any nodes are found, gamma tracing will be performed to determine the radioactive status.

Step 3) Pathological imaging:

The fluorescence and/or radioactive status of all excised nodes will be confirmed *ex vivo* on the back table using both a closed-field imaging device and an open-field device as well as the gamma probe, respectively. Hereafter all excised nodal specimens will be sent for (histo-)pathology. After the tissue has been processed and evaluated by the pathologist, imaging findings will be compared to gold-standard histological-assessment performed by the pathologist (including a hematoxylin and eosin (H&E) staining) to determine the correlation between fluorescence, radioactivity and the presence/absence of tumor tissue in the LN(s). Also findings will be compared to preoperative lymphoscintigraphy and SPECT/CT imaging (ie, correlation between preoperative imaging findings and intraoperative imaging findings).

Neck dissection only (T1-4, cN+)

After the neck has been opened by the surgeon, it will be inspected by the surgeon for the presence of suspicious nodes. Real-time fluorescence imaging of the LNs in the neck will then be performed at 4 time points:

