4. TREATMENT PLAN

4.1 Treatment Schedule

Subjects will receive intravenous panitumumab-IRDye800 (50 mg) 1 to 5 days prior to surgery. Then on the day before surgery, subjects in Cohort 1 will receive a local injection with 2 mCi Lymphoseek followed by lymphoscintigraphy and SPECT/CT imaging to determine the number and location of LNs. In the operation theatre, using a combination of fluorescence imaging and radio-tracing, the LNs of the neck will be evaluated and scored (Section 2.4, Figure 1).

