12.1.3. Sample Size Justification and Power Considerations

We expect to enroll 10 T1/T2 node-negative subjects and 10 subjects with T1-4 and LN metastasis. Based on the data on LN collection from our current IRB-35064 study, we expect that 50% of subjects will undergo a bilateral neck dissection, meaning we would have a total of 30 necks. Assuming an average of 20 LN harvested per neck we would have a total of 600 LNs. Based on previous findings from our IRB-35064 study, we expect approximately 30-40% of subjects (6 to 8 of 20) will have metastatic LNs with an overall prevalence of 5 to 10% of the total number of harvested LNs (30 to 60 of 600) being tumor-positive.

Since this is a Phase 2 study, power considerations are limited but even so, we have excellent power to detect differences in specificity. Although we will use Durkalski's test to compare sensitivities and specificities, we estimated power by first determining the effective sample size (ESS), adjusting for the correlation of LNs within person, and then estimated power using McNemar's test on this ESS. We assumed an intra-class correlation of 0.005, yielding an effective sample size of 524 LNs. With an effective sample size of 524, a prevalence of 7.5%, a significance level of 0.05, and a 0.25 proportion of discordant pairs, we have greater than 99% power to detect a 0.1 difference in specificities, assuming the lower specificity is 0.8. Similarly, we have greater than 78% power to detect a 0.2 difference in sensitivity with the one-sided McNemar test. This assumes the proportion of discordant pairs is 0.25 and the lower sensitivity is 0.75.

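### The primary analysis is assigned a paired significance test, but it has one index test, no second test across both cohorts and no null value

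*Combined protocol and SAP*

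**What the plan says.** Section 12.1.1 calculates the sensitivity and specificity of the intraoperative fluorescence reading, with histopathology as gold standard. It then applies Durkalski's matched-pair test, "accounting for the cluster-correlation within subject, for all sensitivity and specificity comparisons (primary and secondary"), and adds that "Significance for both primary and secondary analyses will be assessed at the 0.05 level". The same sentence promises that "95% confidence intervals will be provided for all estimates", without naming an interval method.

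The design sections name comparators in general terms. Section 2.1 proposes to "directly compare fluorescence imaging of panitumumab-IRDye800 imaging findings to that of SNB and neck dissection", and Section 2.4 says "Panitumumab-IRDye800-based findings will be compared to LN biopsy and neck dissection". Section 4.1 limits the second tracer: "subjects in Cohort 1 will receive a local injection with 2 mCi Lymphoseek". Gamma tracing is likewise Cohort 1 only (Section 9.2.4).

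Section 12.1.3 bases power on McNemar's test for paired differences, for example "power to detect a 0.1 difference in specificities, assuming the lower specificity is 0.8". It does not say which two tests differ.

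The synopsis reads differently. It answers the primary objective by calculating sensitivity and specificity, mentions no test, and places the comparison with Lymphoseek under the secondary objective.

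**The concern.** A matched-pair test asks whether two tests, read on the same nodes, differ in sensitivity or specificity. The primary analysis has one test and a reference standard. With no partner and no null value, the analyst would either have to choose a comparator after the data are in or report a p-value that does not address whether fluorescence identifies metastatic nodes.

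The confidence intervals then become the real primary inference. Section 12.1.1 mentions clustering only for the paired test, and that test gives no interval for a single proportion. Whether the intervals will allow for several nodes from one subject is left open.

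**Working it through.** **1. Is there a second test?** The candidates in the documents are:
- *Lymphoseek and gamma probe*: Cohort 1 only, and already the subject of the secondary objective.
- *Neck dissection*: supplies tissue; node status comes from histology, which is the reference.
- *Repeat fluorescence readings* (in situ, then ex vivo on open-field and closed-field devices, Section 2.4.3.3): present in both cohorts, but they re-read the same index test, and Section 12 does not name them as comparators.

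None is a second test across both cohorts.

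**2. The plan's own figures.** Inputs from Section 12.1.3: 600 nodes, 20 subjects (30 nodes each), ICC 0.005, prevalence 7.5%, discordance 0.25.
- Effective sample size: 600 / (1 + 29 × 0.005) = 600 / 1.145 = 524.0. The plan states 524.
- Negative nodes: 524 × 0.925 = 484.7. Exact McNemar power for a 0.1 difference is 0.993 two-sided and 0.997 one-sided. The plan states more than 99%.
- Positive nodes: 524 × 0.075 = 39.3. One-sided exact power for a 0.2 difference is 0.768 with 39 nodes and 0.782 with 40. The plan states more than 78%.

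The arithmetic reproduces. The powered contrasts are 0.8 against 0.9 and 0.75 against 0.95, so both tests are imperfect. Neither contrast is fluorescence against histology, and 0.75 and 0.8 are power assumptions, not null values.

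**3. What if histology were the partner?** The documents do not say so; this shows only what that reading would give. Within tumor-positive nodes histology is always right, so every discordant pair is a miss by fluorescence.
- Ignoring clustering, with 45 positive nodes: sensitivity 0.95 gives 2 misses, p = 2 × 0.5² = 0.50. Sensitivity 0.75 gives 11 misses, p = 2 × 0.5¹¹ = 0.001.
- With clustering (simulated; assumed 7 subjects × 6 positive nodes; statistic (Σd)²/Σd² against 3.84, d = misses per subject): rejection in about 1%, 24% and 71% of trials at miss rates of 2.8%, 10% and 20% with ICC 0.005, and about 0.3%, 11% and 50% with ICC 0.1.

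Such a test shows only that sensitivity is below 1. If all 600 nodes were paired instead, it would compare false positives with false negatives. Sensitivity 0.972 and specificity 0.927 (the cetuximab-IRDye800 values in Section 2.1) give 41 against 1, z = 40/√42 = 6.2. A poor test with sensitivity 0.20 and specificity 0.935 gives 36 against 36, z = 0. Neither result answers the objective.

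**4. How much does clustering matter for the intervals?** Wilson 95% interval on n/DE, with DE = 1 + (m − 1) × ICC, the form behind the plan's 524. ICCs above 0.005 are assumptions.

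The sensitivity example is 38/42 nodes with m = 6 (7 × 6 = 42, within the plan's 6 to 8 subjects and 30 to 60 positive nodes). The specificity example is 92.7% on 277 negative nodes in 10 Cohort 2 subjects, m = 27.7. The 277 comes from 10 × 30 × 0.925 = 277.5, assuming full dissections and the overall prevalence.

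| ICC | Sensitivity DE | Sensitivity interval | Specificity DE | Specificity interval |
|---|---|---|---|---|
| none | 1 | 77.9-96.2% | 1 | 89.0-95.2% |
| 0.005 | 1.025 | 77.7-96.3% | 1.13 | 88.7-95.3% |
| 0.1 | 1.5 | 74.3-96.9% | 3.67 | 84.5-96.7% |
| 0.2 | 2.0 | 71.1-97.3% | 6.34 | 81.1-97.4% |
| 0.3 | 2.5 | 68.2-97.7% | 9.01 | 78.1-97.8% |

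In simulation at true sensitivity 90% (7 × 6), the unadjusted interval covers in about 92%, 87% and 82% of trials at true ICC 0.1, 0.2 and 0.3. An interval with ICC fixed at 0.2 covers in about 94% to 98% over the same range.

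**The case against.** The best defense is that the wording is loose rather than wrong. The synopsis treats the primary analysis as estimation, Section 12.1.1 also speaks of calculating the two measures, and the test is attached to comparisons, which exist only under the secondary objective. This is a plausible account of the intention. It does not remove the problem, because Section 12.1.1 names the primary analysis twice, once for the paired test and once for the 0.05 level. It does mean that the remedy is to align two sections, not to redesign the study.

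Three stronger readings are tempting, and the documents do not support them:
- *That the plan tests fluorescence against histology and so rewards a worse agent.* No text names histology as the partner, and the powered contrasts, with both tests below 1, point away from it. The behavior in step 3 also depends on pairing within tumor-positive nodes.
- *That the intervals will ignore clustering.* The plan is silent on the method, in a paragraph that recognizes within-subject correlation. At its only ICC the effect on sensitivity is negligible.
- *That no second reading of any kind exists.* Fluorescence is re-read ex vivo in both cohorts; what is missing is a second test.

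**Conclusion.** The point holds for the significance test. As written, the primary paired test at 0.05 has no partner across both cohorts, no null value and no power calculation of its own. This follows from the text and needs no assumption.

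The consequence is bounded: the study is described as exploratory (Section 2.4.1), and the planned sensitivity and specificity estimates remain usable.

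The interval point is conditional. It is immaterial for sensitivity at ICC 0.005. At an assumed ICC of 0.2 the interval widens from about 18 to 26 points for sensitivity and from about 6 to 16 points for specificity. The documents give no basis for judging whether an ICC that large is likely.

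**What to change.** In Section 12.1.1, remove the paired test and the 0.05 statement from the primary analysis, in line with the synopsis, and limit Durkalski's test to two-test comparisons under the secondary objective. Suggested replacement:

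> Node-level sensitivity and specificity of intraoperative fluorescence against histology will be reported by cohort with 95% Wilson intervals on n/DE, where DE = 1 + (m − 1) × ICC and m is the size-weighted mean number of nodes of that class per subject. One ICC per measure, fixed before analysis, is primary; results over ICC 0.005 to 0.3 will be shown as a sensitivity analysis.

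The primary ICC for each measure must be written in before the data are examined. For sensitivity, 0.2 is a workable choice on the coverage shown above. Other intervals that respect clustering by subject would also serve.

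Report by cohort because Cohort 1 nodes are excised mainly for being radioactive ("This process will be repeated until no radioactive nodes are detected anymore", Section 2.4.3.3), so fluorescence accuracy there describes a selected set of nodes. The plan should say so.

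If a primary significance statement is wanted, prespecify the value that the lower limit must exceed. In Section 12.1.3, state that the McNemar power refers to a two-test comparison and not to the primary analysis.

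The cost is SAP wording, a little programming and wider intervals. If the true ICC is near 0.005, a fixed 0.2 is conservative, with coverage of about 99% for sensitivity. No study procedure changes.
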